**Table 5. Data Handling Rules for Primary Endpoint Analysis**

Analyses	Death within 104 days (90 days + 14 days)	Visit out of window	No 90-day (<math>\pm</math> 14 days) visit data
Primary analyses	As if an event occurred	Observed measurements for out-of-window visits will be treated as 90-day results	Multiple imputation*
Sensitivity Analyses1	As if an event occurred	As No Event	As if an event occurred
Sensitivity Analyses 2	As if an event occurred	As No Event	As No Event

\*If percentage of missing primary endpoint is less than 5%, multiple imputation will not be performed and missing data will be regarded as no event.

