7.1.1 Test level

Two-sided tests are performed for all hypothesis tests ($\alpha = 0.05$). The confidence level of all confidence intervals is 95%.

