7.1.3 Estimation of sample size

This study hypothesizes that MMA embolization may reduce the recurrence (operation group) or progression (conservative treatment group) of SDH. The estimated recurrence or progression rate of hematoma in the MMA embolization group is 5%, while that of control group is 12%. When estimating bilateral 5% for the statistical significance level, 90% for power, and 8% for an acceptable rate of loss to follow-up, the total sample size is estimated to be 722 cases.

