## 8.2. Specifications of Primary Efficacy Endpoints Analyses

### 8.2.1. Definitions and Derivations

- **Symptomatic** SDH recurrence (in the trepanation/drainage group) refers to a situation in which the maximum thickness of hematoma of patients exceeds 10 mm, combined with neurological symptoms, or the need for repeat surgery.
- Symptomatic SDH progression (in the non-trepanation/drainage group) refers to a situation in which the maximum thickness of increases by more than 3 mm compared with baseline, combined with neurological symptoms, or the need for surgery.
- The results of central imaging evaluation and analysis of CT/MRI examinations required for the determination of the subject 's primary endpoint in this study will be presented in tables and listings, respectively. Central image evaluation will be performed by the independent Core Lab. Evaluation of neurological symptoms will be derived from the Outcome Assessment Committee (OAC) review data.
- It should be noted that if there is a record of reoperation in participants who have undergone trepanation/drainage, and there is a record of surgical treatment in subjects who have received medical therapy without trepanation/drainage, the occurrence of the primary endpoint can be directly determined, and hematoma thickness or neurological symptoms are no longer required.
- In case of non-negligible amounts of missing data (>5%), we will use the MCMC method based on the Missing at random (MAR) assumption to impute missing data. The regression model will include group, sex, age, BMI, baseline mRS score and baseline maximum

hematoma thickness. The number of imputations is 10, seed=1234, nbiter=200. SAS code examples for multiple imputation will be provided in Appendix 3.

- Hematoma recurrence (trepanation/drainage group) or symptomatic hematoma progression (non-surgical group) at day 90 will be analyzed as follows. If there is any discrepancy between EDC and central imaging assessment scan date in the determination of visit window, the date determined by central imaging assessment shall prevail.

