#### **SAS Code Sample:**

```
proc mi data=im1 seed=1234 n impute=20 out=im2
round=....1
min=....0
max=....1;
;
by trtan;
var sex age bmi basemrs basemth aval;
mcmc chain=multiple nbiter=200 niter=100;
run;
```

```
proc sort data=im2;
```

```
by _imputation_ trtan usubjid siteid;
run;
```

```
proc transpose data=im2 out=im2_t(rename=(_name_=avisit coll=aval));
```

```
by _imputation_ trtan usubjid siteid;  
var v1 v2;  
run;
```

```
proc sql noprint;  
create table im2_count as  
select distinct  
    _imputation_,  
    trtan,  
    avisit,  
    aval,  
    count(*) as count  
from im2_t  
group by _imputation_,trtan,avisit,aval  
order by _imputation_,trtan,avisit,aval  
;  
quit;
```

```
/*clopper-pearsen 95%ci*/  
ods select none;  
proc freq data= im2_count;  
    by _imputation_ trtan avisit;  
    table aval / binomial (cl=exact) alpha=0.05;  
    weight count;
```

```
ods output binomial=binomial;
```

```
run;
```

```
ods select all;
```

```
proc transpose data=binomial out=binomial_t;
```

```
by _imputation_ trtan avisit;
```

```
var nvalue1;
```

```
id label1;
```

```
quit;
```

```
proc sort data=binomial_t;
```

```
by trtan avisit _imputation_;
```

```
run;
```

```
ods select none;
```

```
proc mianalyze data=binomial_t;
```

```
by trtan avisit;
```

```
modeleffects proportion;
```

```
stderr ase;
```

```
ods output parameterestimates=binomial_t_pool;
```

```
run;
```

```
ods select all;
```

```
/*mn*/
```

```
proc freq data=im2_t;  
  by _imputation_ ;  
  tables trtan *aval / commonriskdiff (cl=score test=score) riskdiff (cl=mn);  
  ods output commonpdifftests=commonpdifftests1 commonpdifff=commonpdiffl  
    pdiffcls=pdiffcls1 riskdiffcol1=riskdiffcol11;  
run;
```

```
data riskdiffcol11;  
set riskdiffcol11(where=(row="difference"));  
run;  
proc sort data=riskdiffcol11;  
  by _imputation_ ;  
run;
```

```
proc mianalyze data=riskdiffcol11;  
  modeleffects risk;  
  stderr ase;  
  ods output parameterestimates=pest1_pool;  
run;
```

```
/*cmh*/
```

```
*** perform cmh test;  
proc freq data=im2_t;
```

```
tables strata*trtan*aval/cmh;  
ods output cmh=cmh;  
by _imputation_;  
run;  
*** apply wilson-hilferty transformation to the cmh statistic and  
standardize the resulting normal variable;
```

```
data cmh_wh;  
set cmh(where=(alhypothesis="general association"));  
cmh_value_wh=((value/df)**(1/3) - (1-2/(9*df))/sqrt(2/(9*df));  
cmh_sterr_wh = 1.0;  
run;
```

```
*** combine results;  

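### Both sensitivity analyses for the primary endpoint turn out-of-window events into non-events, and the planned imputation of the 0/1 endpoint (normal draws, then rounding) does not reproduce the event rates

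*SAP*

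**What the plan says.** SAP Table 5, repeated in Appendix 3, gives three sets of rules for the 90-day endpoint. In all three, death within 104 days is an event. They differ as follows.

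| Analysis | Visit out of window | No visit data at day 90 ± 14 |
|---|---|---|
| Primary | observed result used | multiple imputation, or no event if under 5% missing |
| Sensitivity 1 | no event | event |
| Sensitivity 2 | no event | no event |

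The primary row reads "Observed measurements for out-of-window visits will be treated as 90-day results". The footnote on low missingness reads "multiple imputation will not be performed and missing data will be regarded as no event".

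SAP 8.2.1 adds that a recorded re-operation (trepanation patients) or operation (conservatively treated patients) settles the endpoint without imaging or symptoms. Table 5 does not refer to that rule.

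For the imputation, SAP 8.2.1 names an MCMC method under missing at random with group, sex, age, BMI, baseline mRS and baseline thickness. It states: "The number of imputations is 10, seed=1234, nbiter=200". The Appendix 3 sample code begins "proc mi data=im1 seed=1234 n impute=20 out=im2", runs by arm, lists "var sex age bmi basemrs basemth aval", and includes round, minimum 0 and maximum 1 options. The trepanation stratum appears in neither list, although SAP 8.2.1 defines the endpoint differently by stratum and SAP 8.2.2 stratifies the CMH test on it.

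**The concern.** A sensitivity analysis should vary what is assumed about outcomes that were not observed. Here both of them overwrite outcomes that were. The window is ±14 days, so a visit on day 70 is out of window yet inside the 90-day endpoint period; a symptomatic recurrence seen then counts in the primary analysis and becomes a non-event in both checks. Sensitivity 1 is also inconsistent within itself. A patient whose only visit is late fits both the out-of-window column and the no-data column, and the two columns give opposite outcomes.

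The imputation raises a separate question. A normal model for a rare 0/1 variable, followed by rounding at 0.5, need not return the event rate it was fitted to, and the error differs between arms when the rates differ. At stake is the primary estimate itself whenever more than 5% of endpoints are missing.

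**Working it through.** **Plan's own figure.** Inputs from Protocol 7.1.1 and 7.1.3: 12% versus 5%, two-sided α 0.05, and "90% for power, and 8% for an acceptable rate of loss to follow-up, the total sample size is estimated to be 722 cases".

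n per arm = [1.960·√(2·0.085·0.915) + 1.2816·√(0.12·0.88 + 0.05·0.95)]² / 0.07² = (0.7730 + 0.5015)² / 0.0049 ≈ 331.5, so 332.

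332 / 0.92 = 360.9, so 361 per arm and 722 in total. This matches, so 12%, 5% and 8% are the plan's working values.

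**Imputed event rate.** For an arm with rate p, the fitted normal has mean p and variance p(1−p) (covariates ignored).

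- Rounding only: P(event) = P(X > 0.5).
  - p = 0.05: SD 0.218, z = 0.45/0.218 = 2.065, giving 1.95%.
  - p = 0.12: SD 0.325, z = 0.38/0.325 = 1.169, giving 12.1%.
- Draws confined to 0–1, then rounded: P(0.5 < X < 1) / P(0 < X < 1).
  - p = 0.05: 0.0195/0.591 = 3.3%.
  - p = 0.12: 0.1177/0.641 = 18.4%.
- Rounded first, then limits applied: 2.0% and 12.5%.

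| Reading of the code | Embolization | Control | Imputed difference | Overall difference, 8% missing |
|---|---|---|---|---|
| True rates | 5.0% | 12.0% | 7.0 | 7.0 |
| Rounding only | 1.9% | 12.1% | 10.2 | 0.92·7.0 + 0.08·10.2 = 7.25 |
| Round, then limits | 2.0% | 12.5% | 10.5 | 7.28 |
| Confined to 0–1, then round | 3.3% | 18.4% | 15.1 | 0.92·7.0 + 0.08·15.1 = 7.65 |

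With 361 × 0.08 ≈ 28.9 patients imputed per arm, expected imputed events in embolization and control are 1.4 and 3.5 at the true rates, 0.6 and 3.5 with rounding only, and 1.0 and 5.3 with draws confined to 0–1.

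**Simulation.** By-arm normal-regression imputation, 361 per arm, 8% missing, 10 imputations, 1,500 trials. Assumed: 75% surgical, stratum log-odds ratio 1.0. The overall difference was 7.25 (rounding) and 7.57 (confined to 0–1). With Bernoulli draws in place of rounded normals it was about 6.95, matching the full data.

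**Role of the stratum.** With rounding, the imputed difference was 10.1 points with or without the stratum; with draws confined to 0–1 it was 14.4 either way. With Bernoulli draws and missingness depending on stratum, omitting it gave 6.9 against 8.0, a slight attenuation.

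**Other event rates** (imputed difference; rounding only / confined to 0–1):

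- 10% vs 5% (true 5.0): 7.2 / 11.0
- 20% vs 10% (true 10.0): 13.5 / 16.2
- 30% vs 25% (true 5.0): 4.9 / 3.9
- 3% vs 1% (true 2.0): 0.3 / 0.5

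**No difference between arms** (8.5% in both, 3,000 trials, Wald test): no mean bias. Rejection was 5.8% (Bernoulli), 6.5% (rounding) and 7.3% (confined to 0–1), with Monte Carlo standard error about 0.4 points.

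**Out-of-window recoding, Sensitivity 1 and 2.** The documents give no out-of-window share. If a share s applies equally in both arms and every event among those patients is lost, the difference is 7.0·(1 − s): 6.65, 6.3 or 5.6 points at s = 5%, 10% or 20%. These are upper limits on the loss, because operation events may be protected by SAP 8.2.1.

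**No-event rule below 5%.** Up to 36 of 722 missing falls under it (36/722 = 4.99%). With equal missingness, the difference falls no lower than 7.0·0.95 = 6.65. In the extreme, 35 missing all in control gives 12%·(1 − 35/361) − 5% = 5.8 points; all in embolization gives 12% − 5%·(1 − 35/361) = 7.5.

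**The case against.** The best defence is that the primary analysis is sound on visit timing. It uses the observed out-of-window result, and a reader who infers from Table 5 that the primary analysis discards such events is mistaken. The recoding affects only two secondary checks, and a strict-window analysis that ignores a scan on day 105 is defensible, since the endpoint is within 90 days and the window closes at day 104. That stands, but the strict-window reading calls for treating the scan as missing; coding it as a known non-event is a different step, and it also erases early out-of-window events that fall within 90 days.

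A reader might also infer that a re-operation on day 30 is deleted when the 90-day visit slips. The documents do not establish this. SAP 8.2.1 lets a recorded operation settle the endpoint, and such a patient may never reach the out-of-window column. What remains is that precedence is not stated.

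Nor do the sensitivity analyses test nothing. Below 5% missing, Sensitivity 1 still sets missing visits to the opposite extreme; only Sensitivity 2's missing-visit rule is redundant.

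On the imputation, it is fair to say that the code is labelled a sample, that its option list may be damaged in the text, that 8% is an acceptable loss used for sizing and not a forecast of missing endpoints, and that the overall shift is small. None of this removes the problem: every reading tested inflates the difference at the planned rates.

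**Conclusion.** The point holds, with limits. Sensitivity Analyses 1 and 2 code observed out-of-window events as non-events, and Sensitivity 1 contradicts itself between late-seen and unseen patients. Below 5% missing, Sensitivity 2 adds no test of missing visits.

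Above 5%, normal MCMC with rounding misstates the event rates. At 5% versus 12% with 8% missing, the overall difference moves from 7.0 to about 7.25–7.65 points, an excess of 0.25–0.65. This assumes outcomes missing at random at the same share in both arms.

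Two stronger conclusions are tempting and not supported. The omitted stratum does not cause the inflation; its absence is an inconsistency between the imputation model and the stratified analysis. And the imputation does not favour embolization in general: at 3% versus 1% it shrinks the difference, and with equal rates it shows no mean bias.

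The mismatch between 10 and 20 imputations leaves the primary analysis not uniquely specified.

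**What to change.** 1. In both sensitivity rows of Table 5 and its copy in Appendix 3, state that recorded operations, deaths and adjudicated events dated within the endpoint window always count as events. Say explicitly that the operation rule in SAP 8.2.1 takes precedence over the visit-window columns.
2. Handle out-of-window scans in those rows either as observed or as missing under that row's own rule, so that a patient with only a late visit has one defined outcome.
3. Replace normal MCMC and rounding with fully conditional specification using logistic regression, by arm, with the pre-randomization trepanation/conservative stratum in the model. Amend the text of SAP 8.2.1 and the Appendix 3 code together.
4. State one number of imputations in both places.
5. Acknowledge that below 5% missing Sensitivity 2 repeats the primary rule for missing visits. Imputing at any level of missingness would restore the contrast, but that is a preference and not a correction.

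The cost is minor SAP table and code edits, with no new data.

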7.1.4 Estimation of missing values

Missing values are not imputed.

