7.3 Efficacy Analysis

7.3.1 Primary efficacy analysis

Summarize the incidence of the primary endpoint event.

Primary endpoint event: incidence of recurrence (surgery group) or progression (drug therapy

group) of SDH within 90 days post-procedure

Hematoma recurrence refers that the maximum thickness of hematoma exceeding 10 mm, combined with neurological symptoms, or the patient needs to undergo re-operation (surgery group);

Symptomatic CSDH progression refers that the maximum thickness of hematoma increasing by more than 3 mm compared with baseline, or the patient requires operation (drug therapy group).

Note: The primary endpoint event is considered to have been met for any patient who died from any cause within 90 days post-procedure.

Cochran-Mantel-Haenszel (CMH) chi-square analysis will be used for primary endpoints. The difference in event incidence between the two groups and its 95% confidence interval will be calculated. The Kaplan-Meier (KM) method is further used to estimate the incidence of primary endpoint events and its 95% confidence interval.

SAS code to be used in CMH analysis is as follows:

```
ods output CMH=CMH_out;  
  
proc freq data=FatComp order=data;  
  
tables Layer*Exposure*Response /CMH ALPHA=0.05;  
  
weight count;  
  
output out=cmh_ci cmh;  
  
run;
```

Sas code to be used for KM estimation is as follows:

```
proc lifetest data=TTE alpha=0.05;  
  
time avalm*cnsr(1);  
  
strata /group=trtg;  
  
ods output Quartiles = Quartiles
```

```
ProductLimitEstimates=Estimates;  
run;
```

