## 1. Summary of Protocol

### 1.1. Statistical Analysis Plan and Protocol Discrepancies

All changes to the content of the analyses originally specified in Protocol 3.0 (2022-09-21) are summarized in Table 1.

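### Below 5% missing, the SAP's primary analysis counts patients with no outcome data as event-free; this departs from the protocol without being declared and can bias the difference either way if loss is unequal

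*SAP*

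**What the plan says.** Three rules cover the same patient.

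- **Protocol 7.1.4:** "Missing values are not imputed".
- **SAP 8.2.1, more than 5% missing:** "we will use the MCMC method based on the Missing at random (MAR) assumption to impute missing data".
- **SAP Table 5 footnote, repeated in Appendix 3, less than 5% missing:** "multiple imputation will not be performed and missing data will be regarded as no event".

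Exactly 5% falls under neither SAP rule. SAP 1.1 states: "All changes to the content of the analyses originally specified in Protocol 3.0 (2022-09-21) are summarized in Table 1". Table 1 covers the confidence interval methods, the removal of time-to-event analyses, the added regression models, central imaging and event-committee review. It has no entry on missing data.

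Other provisions limit who counts as missing. Death is an event (Protocol 7.3.1; SAP Table 5, through day 104). For a recorded operation or re-operation, SAP 8.2.1 says "the occurrence of the primary endpoint can be directly determined, and hematoma thickness or neurological symptoms are no longer required". In the primary analysis, Table 5 also accepts an out-of-window measurement as the 90-day result.

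Table 5 plans two sensitivity analyses. Sensitivity 1 scores missing as an event and Sensitivity 2 scores it as no event. Both score out-of-window visits as no event.

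**The concern.** Scoring a missing outcome as no event is itself a single imputation, at the favourable extreme. SAP Appendix 2 keeps missing observations in the denominator by default, so an arm's reported rate falls in proportion to its loss. Protocol 11.6 lists CT/MRI for central review only at screening/baseline, day 90 and day 360. A patient who misses day 90 may therefore have no scan that could show a thickness-based event.

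Two things are at stake. Patients know their arm, so loss may differ between arms, and the rule then shifts the primary difference in a direction that cannot be known in advance. The estimator also changes at the 5% line, so a single additional missing patient decides how all the others are handled.

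**Working it through.** **Inputs from the documents.** Event rates 12% control and 5% embolization, two-sided alpha 0.05, 90% power, 8% loss, N = 722 at 1:1 (Protocol 7.1.3 and 3.1; SAP 3). The threshold is 5% (SAP 8.2.1 and Table 5).

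**Assumptions.** The 5% is taken over all randomized patients. The numbers missing and their split by arm are assumed, because the documents give only the 8% planning figure and the threshold. Power is for the unstratified pooled two-proportion test.

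**The plan's own figure.** The pooled-variance formula gives 332 per arm. 332/0.92 = 360.9, so 361 per arm and 722 in total. This matches.

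**Threshold.** 0.05 × 722 = 36.1. With 36 missing (4.99%) the no-event rule applies; with 37 (5.12%) imputation applies. Exactly 5% cannot occur at 722, but it can at a nearby total (36 of 720), and enrollment is only approximate.

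**Effect of the no-event rule.** Reported rate = observed-patient rate × (1 − m), where m is the arm's missing fraction. The SE of the planned difference is √(0.12×0.88/361 + 0.05×0.95/361) = 2.06 points. The table takes lost patients to have the same risk as those observed.

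| 36 missing, control/embolization | Control | Embolization | Difference | Power |
|---|---|---|---|---|
| 18/18 | 0.12×343/361 = 11.40% | 0.05×343/361 = 4.75% | 6.65 points | 90.8% |
| 36/0 | 0.12×325/361 = 10.80% | 5.00% | 5.80 points | 82.5% |
| 0/36 | 12.00% | 0.05×325/361 = 4.50% | 7.50 points | 95.7% |

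For 18/18, an observed-case analysis or valid missing-at-random imputation targets 7.0 points, with power about 91.0%. The bias is 7.0 − 6.65 = 0.35 points, or 0.35/2.06 = 0.17 SE, toward the null.

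**Type I error.** Suppose there is no true effect, both rates are 12%, and all 36 missing are in the embolization arm. The reported rates are 12.0% and 10.8%, a spurious difference of 1.2 points. The two-sided rejection probability is about 8%.

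**What the sensitivity analyses add below 5%.** Sensitivity 2 repeats the primary rule for these patients. Sensitivity 1 goes to the other extreme. With all 36 lost from embolization it gives 12 − (0.05×325 + 36)/361 × 100 = −2.5 points, against 7.5 under the primary rule. It also recodes out-of-window visits, so two rules change at once. Neither is a missing-at-random or observed-case estimate.

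**The SAP's imputation code.** Appendix 3 appears to draw the binary outcome from a normal model by arm and round to 0 or 1 (the line is damaged in the text available). Ignoring covariates, a draw from a normal distribution with mean p and variance p(1−p) exceeds 0.5 with probability about 12% when p = 0.12 and about 2% when p = 0.05. If draws outside 0–1 are redrawn first, these become about 18% and 3%. The imputed difference is then 12 − 2 = 10 to 18 − 3 = 15 points rather than 7, which is away from the null. The text specifies 10 imputations and the code 20. The imputation variables omit the trepanation/drainage stratum, although the CMH test is stratified by it.

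**The case against.** The strongest reply is that the rule is narrow and its effect small. Deaths, recorded operations and out-of-window scans are already used, so only patients with none of these are scored as no event. The rule applies only when retention is better than planned: 8% loss is 0.08 × 722, about 58 patients, which falls under imputation. Balanced loss costs 0.35 points and hardly any power. The threshold is prespecified, Sensitivity 1 gives the opposite extreme, and Protocol 7.1 leaves room for a later SAP. If lost patients are in fact at lower risk, the no-event score may be no worse than the alternative. With balanced 4.9% loss and half the risk among the lost, it gives 6.8 points and observed cases 7.2, against a truth of 7.0.

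All of this stands, and it limits the point. It does not justify assuming the favourable outcome in the primary analysis, nor omitting the change from a table said to be complete. Sensitivity 1 does not supply the missing middle estimate.

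A reader might infer a serious loss of power. If 8% of controls and 1.8% of embolized patients are lost and the lost have twice the risk, power under the rule is 79%. The documents support neither the split nor the doubled risk. Observed-case power in that scenario is already 85%, so much of the fall from 91% comes from outcome-dependent loss, which missing-at-random imputation would not repair.

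**Conclusion.** The concern holds in a limited form and should be corrected. The protocol and SAP conflict on missing primary outcomes, SAP Table 1 does not record it, and the sub-5% rule is biased whenever a missing patient had an event. With equal loss just under 5% the bias is about 0.35 points toward the null, which is negligible for the test. With all 36 missing in one arm, the assumed extreme, the difference runs from 5.8 to 7.5 points. Type I error reaches about 8% in the single null scenario shown.

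Three stronger readings are not supported. Not every patient without a 90-day visit is scored a success, given the provisions for deaths, operations and late scans. The rule does not systematically favour embolization, because equal loss works against it. Nor is the SAP's imputation ready to use at every level of missingness: its sample code, as far as it can be read, could put a bias away from the null in place of a mostly conservative one.

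The finding on Table 1 assumes that the protocol supplied is version 3.0, the version the SAP cites.

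**What to change.** 1. Delete the footnote to SAP Table 5 and its copy in Appendix 3, and remove the 5% condition from 8.2.1.
2. Use multiple imputation for the primary analysis at any level of missingness, with a model for a binary outcome, such as logistic (fully conditional) imputation by arm, in place of rounded normal draws. Include the trepanation/drainage stratum and carry it through to the CMH step. State one number of imputations in both text and code.
3. Keep missing-as-event and missing-as-no-event as sensitivity analyses. Handle out-of-window visits in both as in the primary analysis, so that only one rule changes at a time.
4. Record the departure from Protocol 7.1.4, with its reason, in SAP Table 1.

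The cost is SAP wording and a small amount of programming. No new data are needed and the sample size does not change. Imputation still rests on the missing-at-random assumption, which is why both extreme scorings should stay.
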